16.33 Correlative Research

In addition to the 45 evaluable Grade-IV MGMT Un-methylated patients, these correlative research endpoints will use the combined information from all of the evaluable grade-IV patients. As of 2/16/2017 this sample size will include at least 22 endpoint-evaluable patients with Grade-IV MGMT methylated status and 5 endpoint-evaluable patients with unknown MGMT status. Therefore the minimum sample size for these correlative endpoints is 72 patients. Subgroup analysis will be included as appropriate for these correlative endpoints to assess known prognostic factors such as MGMT and age. To control for multiple testing the false discovery rate (FDR) [75], which is the expected proportion of false discoveries amongst the rejected hypotheses, will be used at a 0.05 level.

16.331 Compare RT treatment volumes defined by MR only with RT treatment volumes defined with both PET and MR information for Grade IV glioma patients.

To assess the impact of integrating PET on target definition, the treating radiation oncologists (Dr. [name], [REDACTED]) will first define the treatment volumes for $\text{GTV}_{1\text{MR}}$ and $\text{GTV}_{2\text{MR}}$ using the MR images while blinded to the PET study. Then the PET contours, using gold standard volumes generated by Drs. [name] or [name] for $\text{GTV}_{1\text{PET}}$ and T/N ratio of >2.0 for $\text{GTV}_{2\text{PET}}$, will be reviewed by the treating radiation oncologist and expanded as described above. The volume of overlap and non-overlap between the GTV_1 and 2 defined by MR and that defined by PET will be calculated. Similarly, the MR-only defined volumes will be compared against the volumes defined with the combination of MR and PET planning. Paired t-test statistical analysis will be performed to determine if any differences exist and the level of statistical significance between treatment volumes defined by MR only and treatment volumes defined with both PET and MR information. The analysis of volumes from the combined 72 Grade IV patients will have 90% power to detect differences in volumes with an effect size of 0.39 using a paired t-test with a 0.05 two-sided significance level. Alternate metrics for comparison will also be assessed, including spatial overlap, distance, correlations and 3D shape comparisons.

16.332 Compare timing of accurate identification of progression defined by ^{18}F -DOPA PET, pMRI and conventional MRI for Grade IV glioma patients.

Both ^{18}F -DOPA PET imaging [6, 9] and pMRI [54] have been shown to differentiate recurrence from pseudo-progression better than conventional MR imaging. There are several reasons why we anticipate ^{18}F -DOPA PET imaging will identify HGG progression earlier than pMRI, and may more accurately differentiate progression from pseudo-progression. As pMRI is based on angiogenesis, it is possible that ^{18}F -DOPA may detect additional separate or complimentary tumor segments

that aren't particularly angiogenic, and could therefore be missed with pMRI. Also, per our preliminary data, ^{18}F -DOPA appears to successfully detect tumor in non-enhancing tissue. pMRI has not been used to characterize tumor in the non-enhancing segment, so there is no historical data to compare ^{18}F -DOPA and pMRI for this tumor segment. For each confirmed incidence of progression per conventional MRI we will review follow-up imaging acquired with PET and pMRI prior to the confirmed progression to determine which modality correctly identified progression earliest. We will compare ^{18}F -DOPA PET with our recently published pMRI-Fractional Tumor Burden method to differentiate regional tumor progression from radiation necrosis and pseudoprogression [68]. To compare the progression identification timing we will calculate the percentage of time each modality was earlier than conventional MRI. With a sample size of 72, if the observed percentage earlier than conventional MRI is 30% for either modality, a two-sided 95.0% confidence interval for a single proportion using the large sample normal approximation will be $\pm 10.6\%$. Progression identification timing will also be compared using Kaplan-Meier methods and paired t-tests to determine if differences exist between the modalities.

- 16.333 Compare patterns of failure after radiation therapy targeting volumes defined with target volumes designed to with both ^{18}F -DOPA PET and conventional MR image information with patterns of failure for historical controls from Mayo Clinic Rochester patients. As described above for confirmed-progression free survival, we will analyze both historical control patients and our prospective dose escalation patients. Imaging archived for the cohort of Mayo Clinic patients used as historical controls for confirmed-progression free survival will be assessed for patterns of failure, to compare with patterns of failure determined for patients treated with ^{18}F -DOPA PET image-guided dose escalation. As noted above, one of our neuro-radiologists, [REDACTED] or [REDACTED], will review all cases to define the date of radiographic progression. The relevant image set will be fused with our treatment planning scan and then the radiologist will contour the region of progression blinded to the dose distribution contour. A volumetric analysis then can be performed to define the doses delivered to the absolute and relative volume of the region where the recurrence is defined. With the close imaging follow-up mandated on clinical trials and for our standard of care, we will be able to robustly evaluate the patterns of failure relative to dose delivered to those regions. Chi-square tests of proportions will be used to test for differences in the proportions of patients with central, in-field, marginal, or distant failures between the patients on this study and historical controls.
- 16.334 Compare RT treatment volumes defined by MR only with RT treatment volumes defined with both PET and MR information for Grade III glioma patients. Paired t-test statistical analysis will be performed to determine if any differences exist and the level of statistical significance between treatment volumes defined by MR only and treatment volumes defined with both PET and MR information.

16.335 Evaluate intra- and inter-observer variability with vs. without the addition of ^{18}F -DOPA PET uptake for radiotherapy target volume delineation. Potential for reduction in inter- and intra-observer variability for RT target delineation with the addition of PET in conjunction with biopsy-validated threshold guidance will be evaluated through volume comparisons of target volumes delineated with MR alone and MR in combination with PET information by our radiation oncologists (Drs. [name], [name] and [name]) as well as gold standard volumes generated by Drs. [name] or [name] for MRI and Drs. [name] or [name] for PET. The concordance correlation coefficient will be used to measure agreement between volumes generated with each method, as well as to evaluate inter-observer variability, where variability associated with MR will serve as the standard for comparison.

Several tools commercially available for semi-automated PET contouring will be investigated for consistency with the biopsy-validated thresholds, to standardize the method of ^{18}F -DOPA PET integration into RT delineation, reducing operator error and subjectivity commonly associated with manual delineation of target volumes utilizing PET data. The variation of PET volumes defined with different segmentation techniques will be evaluated, including manual visual delineation, SUV-based delineation using an isocontour of $\text{SUV} = 2.5$, fixed threshold techniques ranging from 40-80% of the maximum signal intensity in the primary tumor, adaptive threshold delineation using the source-to-background ration (SBR) technique, and the PET Edge gradient technique in the MIM software package.

16.336 Compare timing of accurate identification of progression defined by ^{18}F -DOPA PET, pMRI and conventional MRI for Grade III glioma patients. In addition to Grade IV patients analyzed above, progression identification will also be made for the Grade III patients and analysis will include determination of any differences between Grade IV and III patients. Progression identification timing will be compared using Kaplan-Meier methods and paired t-tests to determine if differences exist between the modalities. An exploratory analysis of DTI for detecting invasive non-enhancing tumor recurrence will also be performed.

16.337 Compare predictive capabilities of ^{18}F -DOPA PET, pMRI and DTI for localization of recurrences for patients treated with ^{18}F -DOPA PET-guided RT dose escalation. Predictive capabilities of ^{18}F -DOPA PET, pMRI and DTI for localization of recurrences for patients treated with ^{18}F -DOPA PET-guided RT dose escalation will be compared by identifying the recurrence volume with each modality and correlating with identification of aggressive disease in the pre-RT planning images.

16.4 Data and Safety Monitoring Plan:

16.41 The Study Chairs and the study statistician will review the study at least twice a year to identify accrual, adverse event, and any endpoint problems that might be developing. The Mayo Clinic Cancer Center (MCCC) Data Safety and Monitoring Board (DSMB) is responsible for reviewing the accrual and safety for this trial at least twice a year, based on reports provided by the MCCC Statistical Office.

16.42 Adverse Event Stopping Rules:

As no reactions to ^{18}F -DOPA have been reported within the institution, toxicity testing reported in the literature revealed no deleterious effects (section 15.0), and there have been no allergic reactions in all patients accrued to date to the pilot study (MC1078), no reactions are anticipated. As such, at any point in the enrollment process after 10 or more patients have been enrolled, if more than 10% of these patients enrolled are unable to complete PET scanning due to allergic reactions to the tracer, enrollment will be suspended so that details of each episode can be examined and a trial recommendation will be formulated and presented to the MCCC DMC.

There have been no reports in the literature of the occurrence of NSF in patients with normal renal function [62, 69]. Additionally, we will use the contrast agent gadobenate dimeglumine, which has been shown to have a high safety profile (lower incidence of NSF in patients with renal failure/insufficiency) compared with many other available Gd-based contrast agents [62, 69]. Therefore no reactions are anticipated. As such, if at any time a patient develops NSF enrollment will be suspended so that details of the episode can be examined and a trial recommendation will be formulated and presented to the MCCC DMC.

Using the dose escalation approach described in [Section 7](#), previous studies have successfully dose escalated to 76 – 80 Gy without significant increases in acute or late adverse effects [51]. Nonetheless, both acute (available at <http://ctep.cancer.gov>) and late [71] toxicity will be monitored continuously as each patient is accrued and follow-up data are accumulated. As such, at any point in the enrollment process after 10 or more patients have been enrolled, if more than 10% of these patients enrolled experience any of the following adverse events considered to be at least possibly related to treatment, enrollment will be suspended so the details of each episode can be examined and a trial recommendation will be formulated and presented to the MCCC DMC, adjusting the PTV3 escalated dose level if necessary.

- Grade 3 or 4 irreversible CNS toxicity
- Grade 4 non-hematologic, non-CNS toxicity
- Any Grade 5 toxicity

16.5 Results Reporting on ClinicalTrials.gov:

16.51 Initial estimated Primary Completion Date: At study activation, this study will have been registered within the www.ClinicalTrials.gov (CT.gov) website. The Primary and Secondary endpoints along with other required information for this study will be reported on CT.gov. For purposes of timing of the CT.gov results reporting, the initial estimated completion date of the primary endpoint of this study is 60 months after the study opens to accrual.

16.52 Definition of Primary-Endpoint Completion Date (PCD): The PCD is the date at which the last confirmed-progression free patient has been followed for 6 months.

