16.2 Statistical Design

16.21 Decision Rules

An endpoint-evaluable patient is defined to be a patient that is treated with ^{18}F -DOPA PET image-guided dose escalation RT. The primary endpoint is the proportion of grade-IV MGMT un-methylated patients treated with ^{18}F -DOPA PET image-guided dose escalation RT who are alive and do not have confirmed progression within 6 months from the time of craniotomy. A success will be a patient who is alive and does not have confirmed-progression within 6 months from the time of craniotomy. At Mayo Clinic, the 81 Grade IV MGMT un-methylated patients accrued to the two trials listed above, combined with the 14 similar patients not treated on clinical trials had a combined rate of CPFS6 of 59.3%. These patients were newly diagnosed grade-IV MGMT un-methylated patients treated with 3D-conformal or IMRT with TMZ. Therefore the largest success proportion where the proposed treatment regimen would be considered ineffective in this population is 60%, and the smallest success proportion that would warrant subsequent studies with the proposed regimen would be 72.5%. The following Simon's Optimum design requires 45 grade-IV MGMT un-methylated patients to test the null hypothesis that the proportion of successes is at most 60% with an overall significance level (α) of 0.20, and a power of 80% to detect a true success proportion of 72.5%.

16.211 Stage 1: If 15 or fewer successes are observed in the first 25 grade-IV MGMT un-methylated evaluable patients that have been followed for at least 6 months, we will consider this regimen to be ineffective in this patient population. If 16 or more successes are observed in the first 25 evaluable patients we will continue accrual and results will wait until the final analysis.

16.212 Stage 2: After 45 evaluable grade-IV MGMT un-methylated patients are accrued to this study and followed for at least 6 months, if 30 or more successes are observed in the first 45 evaluable patients, we may recommend further testing of this regimen in subsequent studies in this patient population.

16.213 Over Accrual: If more than the target number of Grade-IV MGMT un-methylated patients are accrued, the additional patients will not be used to evaluate the stopping rule or used in any decision making process.

16.214 Note: We will not suspend accrual between stages to allow the first 25 patients to become evaluable, unless undue toxicity is observed.

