16.22 Sample Size

The two-stage design to be utilized is fully described in Section 16.21. A minimum of 25 and a maximum of 45 Grade-IV MGMT un-methylated evaluable patients will be accrued to this phase-II study unless undue toxicity is encountered. We anticipate accruing an additional 5 Grade-IV MGMT un-methylated patients to account for ineligibility, cancellation, major treatment violation, or other reasons. We also anticipate accruing a total of 25 Grade-IV MGMT methylated, 12 Grade-IV patients with unknown MGMT status, and 6 grade-III patients. Maximum projected accrual is therefore 87 grade-IV patients and 6 grade-III patients. We anticipate pre-registering 150 patients to register these 93 patients necessary for the study design.

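### The stated minimum of 72 for the correlative analyses holds only if stage 2 completes, and the zero-difference t-test on target volumes does not show how much PET adds

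*Combined protocol and SAP*

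**What the plan says.** Section 16.33 pools all evaluable Grade IV patients for the correlative endpoints. To the 45 un-methylated patients it adds "at least 22 endpoint-evaluable patients with Grade-IV MGMT methylated status and 5 endpoint-evaluable patients with unknown MGMT status", counted on 2/16/2017, and concludes: "Therefore the minimum sample size for these correlative endpoints is 72 patients". Two calculations use that number. Section 16.331 says the 72 patients "will have 90% power to detect differences in volumes with an effect size of 0.39" in a paired t-test at two-sided 0.05. Section 16.332 gives a 95% half-width of ±10.6% for an observed 30%.

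The un-methylated count is not fixed at 45. Section 16.22 states: "A minimum of 25 and a maximum of 45 Grade-IV MGMT un-methylated evaluable patients will be accrued". Section 16.211 sets the stage 1 rule: "If 15 or fewer successes are observed in the first 25 grade-IV MGMT un-methylated evaluable patients", the regimen is considered ineffective. Section 16.214 keeps accrual open while the first 25 mature. On the other groups 16.22 says: "We also anticipate accruing a total of 25 Grade-IV MGMT methylated, 12 Grade-IV patients with unknown MGMT status".

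For target volumes, 16.331 says: "Paired t-test statistical analysis will be performed to determine if any differences exist and the level of statistical significance between treatment volumes". The comparison is of MR-only contours against contours that use MR together with PET. It also plans other measures: "The volume of overlap and non-overlap between the" MR-defined and PET-defined GTVs is to be calculated, and spatial overlap, distance and shape are listed as alternate metrics. Figure 8 in 7.41 forms each combined GTV as a Boolean sum of the MR and PET GTVs and sets GTV7600 equal to GTV6000. Section 16.334 applies the same t-test to Grade III, where 16.321 counts 4 evaluable patients and 16.22 anticipates 6.

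**The concern.** There are two separate problems.

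First, a total that contains the design's maximum for its largest group is called a minimum. If the trial stops at stage 1, the correlative analyses may have fewer than 72 patients, and the stated power and precision would not apply. Section 16.24 puts the chance of that stop at 0.575 if the true success rate is 60%.

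Second, 16.331 sets out to assess the impact of adding PET to target definition, and this is the only powered analysis of that question. What it powers is a test of zero mean difference between a volume and the union of that volume with another. Rejection says that PET added something in some patients. A radiation oncologist would want to know how much was added, and the plan names no estimate with a confidence interval for it.

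The Grade III version has a further difficulty: with 4 to 6 patients, a non-significant result would be hard to interpret.

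**Working it through.** **Reproducing the plan's power.** A paired t-test is a one-sample t-test on the differences, with df = n−1 and noncentrality d√n. For n = 72 and d = 0.39, noncentrality is 0.39 × √72 = 3.31 and the two-sided 5% critical value on 71 df is 1.994. Power is 90.4%, so the plan's 90% is right. At n = 71 it is 89.99%, so 72 is the smallest n that reaches 90% and there is no slack.

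**Reproducing the half-width in 16.332.** 1.96 × √(0.3 × 0.7 / 72) = 0.106, which matches ±10.6%.

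**Stage 1 stop.** P(15 or fewer of 25) is 0.575 at a true rate of 60% and 0.122 at 72.5%, matching the table in 16.24.

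**Possible N.**
- Floor after a stage 1 stop: 25+22+5 = 52.
- Overrun (assumption): the first 25 need 6 months of follow-up and 16.23 plans 14 un-methylated patients a year, so 14 × 0.5 = 7.
- With overrun and the current 22 and 5: 32+22+5 = 59.
- With overrun and all 25 methylated and 12 unknown-status patients evaluable: 32+25+12 = 69.
- Reaching 72 after a stop would need all 37 of those patients plus 35 un-methylated, an overrun of 10.
- Floor if stage 2 completes: 45+22+5 = 72.

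| N | Power at d = 0.39 | Half-width at 30% |
|---|---|---|
| 52 | 78.8% | ±12.5% |
| 59 | 83.8% | ±11.7% |
| 69 | 89.1% | ±10.8% |
| 72 | 90.4% | ±10.6% |

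**The volume test.** For unedited GTVs, (MR ∪ PET) − MR is the PET volume lying outside MR, which is zero or positive in every patient. The mean difference is zero only if PET adds nothing in anyone.

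How often the test would reject depends on how many patients have added volume. The documents give no distribution, so I assumed two shapes and simulated 40,000 trials at n = 72, with k patients having a positive increment and the rest zero (two-sided p<0.05, no multiplicity adjustment):

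| k | Exponential | Log-normal (log-SD 1) |
|---|---|---|
| 4 | 1.7% | 2.3% |
| 6 | 46% | 49% |
| 8 | 82% | 76% |
| 10 | 95% | 88% |
| 15 | 99.8% | 97% |

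At n = 52 with k = 10 and 15 the rates are almost the same. They do not depend on the mL scale. The false discovery rate control in 16.33 could lower them.

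The added-volume interval needs no new data. Its half-width is t(0.975, n−1)/√n in units of the SD of the differences: 0.278 at 52 and 0.235 at 72.

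**Grade III.** If the Grade IV effect size of 0.39 applied, power would be 8.7% at n = 4 and 12.3% at n = 6.

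**The case against.** The strongest reply on sample size is that 90% is correct for the planned full accrual and that 52 is a worst case. It requires no overrun and no further methylated or unknown-status patient after 2/16/2017, whereas 16.214 and 16.22 point the other way. That stands. A reader might infer that the power calculation is wrong, or that 52 is the expected number after a stop. The documents support neither. The plausible loss after a stop is about 1 to 7 points of power (90.4% against 89.1% to 83.8%), and only the word minimum is wrong.

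On the volume test, a reader might infer that it is bound to reject or carries no information. That is too strong. If only 4 patients had added volume it would reject in about 2% of trials, and with 6 in under half. Physician modification of CTVs (7.41) and the review notes in Figure 8 also mean that the union argument is firm only for unedited GTVs.

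Nor does the pilot settle the matter. Section 1.6 reports PET volume above the threshold outside contrast enhancement (15–81%) in 6 enhancing patients. Those scans were pre-operative and compared with enhancement alone. The 51 Gy MR GTV also includes FLAIR, and its PET counterpart is not the T/N>2.0 volume, so the pilot is no direct evidence at that level. At the 60/76 Gy level, resection and the cavity change both volumes.

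It is also fair that overlap and non-overlap volumes are already planned. What is missing is a named main estimate with an interval.

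For Grade III, 0.39 was set for Grade IV. A much larger effect could be detected (at d = 1.5, n = 6 gives 83%), and 1.8 says many, not all, Grade III endpoints are affected.

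**Conclusion.** The concern holds in limited form. The figure of 72 is a minimum only if stage 2 completes; from the plan's own numbers the guaranteed floor is 52. Power at d = 0.39 is then 78.8%, or about 84–89% at the more likely 59–69. That range assumes about 7 overrun patients and, at its upper end, that all anticipated methylated and unknown-status patients are evaluable.

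For unedited GTVs the direction of the difference is fixed in advance. The powered test is likely, though not certain, to reject, and rejection would not measure PET's impact. The rejection rates rest on assumed shapes for the added volume. With 4 to 6 Grade III patients, a t-test adds little to a description.

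All of this concerns correlative goals. The CPFS6 decision rule and its operating characteristics are not affected.

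**What to change.** - **16.33:** replace the stated minimum with: at least 52 Grade IV patients (25+22+5) if the trial stops at stage 1, probably about 59–69 with continued accrual, and at least 72 (45+22+5) if stage 2 completes.
- **16.331, power:** give 78.8% at 52 and 90.4% at 72.
- **16.332:** give the half-width as ±12.5% at 52 and ±10.6% at 72.
- **16.331, main result:** report the mean added volume with 95% CI, in mL and as a percentage of the MR volume (mL only where the MR volume is zero). Do this for GTV and for the expanded CTV and PTV at each dose level, since added PET GTV may fall within the MR margin. Keep the paired t-test as secondary.
- **GTV edits:** where available, note edits made after PET review, so that departures from the pure union can be seen.
- **16.334:** list the Grade III values descriptively, without a test.

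Most of this is SAP wording on volumes already to be calculated. Noting edits is a small data-capture task and may not be possible for patients already treated. The downside is that the stated power looks slightly less favourable for a stage 1 stop.

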 - Because of the difficulty determining pseudoprogression from progression, and bevacizumab can be used to treat either progression or radiation-related treatment changes, treatment with bevacizumab alone does not qualify as progression. Clinical progression is determined by treating oncologist or initiation of systemic salvage regimens other than bevacizumab.
 - Cannot be considered Pseudoprogression
- Patients with possible PsP should initially be given the Objective Status of Preliminary Progression.
 - If Progressive Disease is subsequently confirmed, the Objective Status is to be recorded for the current cycle as PD (confirmed) and the back-dated date of the progressive disease (from the cycle with the initial Preliminary PD) is to be used as the date of progressive disease which is documented via the Event Monitoring Form.
 - If progressive disease is not confirmed the Objective Status for the current cycle can be documented as SD, PR, or CR as appropriate using the baseline scan measurement as the baseline for comparison with the current measurements. The Objective Status for the cycle initially documented as Preliminary PD can be changed to PsP.

11.417 Confirmatory Measurement/Duration of Response

11.4171 Confirmation

To be assigned a status of PR or CR, changes in tumor measurements must be confirmed by repeat assessments that

should be performed 4 weeks after the criteria for response are first met.

11.4172 Duration of Overall Response

The duration of overall response is measured from the time measurement criteria are met for CR or PR (whichever is first recorded) until the first date that recurrent or progressive disease is objectively documented (taking as reference for progressive disease the smallest measurements recorded since the treatment started).

The duration of overall CR is measured from the time measurement criteria are first met for CR until the first date that recurrent disease is objectively documented.

11.4173 Duration of Stable Disease

Stable disease is measured from the start of the treatment until the criteria for progression are met, taking as reference the smallest measurements recorded since the treatment started.

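### Section 16.332 gives PET and pMRI no way to be later than conventional MRI, so the paired t-test against MRI and the percentage earlier cannot show a lead time

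*Combined protocol and SAP*

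**What the plan says.** Goal 2.32 asks which of ¹⁸F-DOPA PET, pMRI and conventional MRI identifies Grade IV progression first. Section 16.332 sets out the comparison:

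- Patients enter through MRI: "For each confirmed incidence of progression per conventional MRI".
- The scans read are limited to those before that point: "we will review follow-up imaging acquired with PET and pMRI prior to the confirmed progression to determine which modality correctly identified progression earliest".
- The summary is one-directional: "we will calculate the percentage of time each modality was earlier than conventional MRI".
- Precision is illustrated as follows: "With a sample size of 72, if the observed percentage earlier than conventional MRI is 30% for either modality", with a 95% half-width of 10.6 percentage points.
- Tests are added: "Progression identification timing will also be compared using Kaplan-Meier methods and paired t-tests to determine if differences exist between the modalities".

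No category is defined for a modality that turned positive after MRI or not at all. No rule is given for coding such a patient in the t-test or the Kaplan-Meier analysis. Section 16.332 also does not say which MRI date is the reference. For possible pseudoprogression that is later confirmed, the notes to the table in 11.416 say "the back-dated date of the progressive disease (from the cycle with the initial Preliminary PD) is to be used as the date of progressive disease".

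Under 13.4 and 13.5, PET scanning continues until progression is confirmed and then stops. A PET at the confirming visit is strongly encouraged.

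**The concern.** The paired t-test is meant to detect a difference in timing in either direction. Under the stated window, the difference (MRI date minus PET or pMRI date) is zero or positive in every patient. A patient in whom PET would have lagged behind MRI becomes a tie or drops out, and never offsets a patient in whom PET led. Testing such a variable against zero comes close to asking whether PET was ever earlier in a handful of patients.

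The percentage earlier has the same weakness. Two equally good modalities with independent reading error will each be ahead in some patients, so a 30% earlier rate fits a real lead and no lead equally well unless the later rate stands beside it.

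At stake is a claim that PET or pMRI brings forward the identification of progression. The false discovery rate control in 16.33 does not help, because it takes the p-values as valid.

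**Working it through.** **Inputs.** From 16.332: n = 72, 30% earlier, 95% confidence. From 16.33: 72 = 45 + 22 + 5 evaluable patients, and a 0.05 level (set for the false discovery rate; no separate level is given for the timing tests). From Section 4.0, note 3: scans about every 2 months in the first year. Assumed, because the documents give none: disagreement rates, reading-error SDs, correlation between modalities, and the number of progressors.

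**1. The plan's own figure.** 1.96 × √(0.30 × 0.70 / 72) = 0.1059, or ±10.6%. It reproduces. It treats all 72 evaluable patients as progressors, which is the best case; with an assumed 58 or 50 progressions the half-width is ±11.8% or ±12.7%.

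**2. How few early calls give significance.** Let k of n patients be one visit earlier and the rest be ties. The one-sample t statistic on the differences reduces to t = √[k(n − 1)/(n − k)]. With n = 72:

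| k earlier | t | two-sided p |
|---|---|---|
| 3 | √(3 × 71/69) = 1.76 | 0.083 |
| 4 | √(4 × 71/68) = 2.04 | 0.045 |
| 22 (about 30%) | √(22 × 71/50) = 5.59 | 4 × 10⁻⁷ |

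If 22 were earlier and 22 later by one visit, t = 0 and p = 1. The plan as written could not tell that case from the last row.

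**3. False declaration under equal performance.** Let each modality be ahead in a proportion q of patients, with later cases coded as ties. By step 2, the false declaration has probability P(X ≥ 4), with X ~ Binomial(72, q):

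| q in each direction | P(PET declared earlier) |
|---|---|
| 2% | 0.06 |
| 5% | 0.49 |
| 10% | 0.94 |
| 15% | 0.997 |
| 20% to 30% | about 1.00 |

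A simulation on the visit grid, where leads may span more than one visit, gives 0.49 at q = 5.5%, 0.90 at 10.5% and 0.998 at 18.8%. When later detections count, the same test rejects in 3% to 5% of trials. Dropping later cases instead of coding them as ties still rejects in 53% to 100% of trials once q is 5.5% or more.

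**4. Fewer progressors.** In a second simulation, true progression is uniform on 4 to 20 months, modalities have independent normal errors with the same SD, detection is rounded up to the next 2-monthly visit, and later cases are ties. Rejection rates:

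| n | SD 0.5 mo | SD 1 mo | SD 2 mo |
|---|---|---|---|
| 20 | 0.30 | 0.73 | 0.91 |
| 30 | 0.62 | 0.96 | 0.99 |
| 50 | 0.93 | 1.00 | 1.00 |
| 72 | 0.99 | 1.00 | 1.00 |

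With later detections allowed, the rate is 0.04 to 0.06 throughout. PET is earlier in 14%, 26% and 37% of patients at the three SDs, with no true lead. The plan's 30% lies inside that range.

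**5. Correlated errors.** The modalities image the same tumour at the same visits. At n = 50 and SD 0.5, rejection falls from about 0.93 to 0.38 at correlation 0.8 and to 0.07 at 0.95. At SD 2 it remains about 1.00 and 0.89.

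**The case against.** **The reference date is undefined, not necessarily wrong.** Sections 16.11 and 16.333 have a neuro-radiologist set the date of radiographic progression, and 11.416 back-dates some confirmed cases. If MRI is dated at first progression and PET is read through the confirming visit, PET can be later. The t-test then rejects in 2% to 6% of trials for mean detection lags up to 1 month, and in 14% at 2 months. Section 7.53 also describes the imaging comparison without the one-sided limit. This stands as a possible reading, but 16.332 does not state it, and its wording points the other way.

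**Kaplan-Meier.** A reader might infer that the Kaplan-Meier comparison also favours PET. The documents do not support that, because the direction depends on an unstated coding rule. Under equal performance, the log-rank test rejects in about 0% of trials with ties. If non-detections are censored at the MRI date, it rejects toward PET being later (0% to 15% when same-visit calls count as detections, about 100% when they do not). If they are dropped, it rejects toward PET being earlier (1% to 25%, depending on the comparison set).

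**PET versus pMRI.** The expectation in 16.332 that PET will precede pMRI is untouched. Both are cut off at the same point, and rejection is 0.2% to 5%.

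**Section 16.336.** A reader might carry the point over to Grade III because "Progression identification timing will be compared using Kaplan-Meier methods and paired t-tests to determine if differences exist between the modalities" appears there too. That section has no one-sided window of its own, and only 4 evaluable (16.321) to 6 anticipated (16.22) patients. Even with the window imported, rejection is about 0.00 to 0.10.

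**Weight.** This is correlative research, the sized quantity is a descriptive percentage, and no decision rule uses it. How often PET was positive before MRI is a fair description; it is not evidence of a lead on its own.

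**Conclusion.** The concern holds for two items in 16.332: the paired t-test of PET or pMRI against conventional MRI, and the percentage earlier than MRI. Followed literally, the t-test is not a valid test of equal timing, and the percentage cannot be interpreted without its counterpart. The size depends on how often equally good modalities disagree: at n = 72 the false declaration is about 0.94 or more (0.90 in the visit-grid simulation) at roughly 10% disagreement in each direction, and negligible at about 2%. Disagreement rates, error SDs and correlation are assumptions.

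It would go too far to say that PET wins whatever the truth: with few disagreements or strongly correlated errors the inflation can be small, and a clearly stated back-dated MRI date with full reading would remove most of it. A change is still warranted, because the result against MRI cannot be trusted as the section is written.

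**What to change.** In Section 16.332:

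1. Date conventional MRI at its first centrally read radiologic progression, using the back-dated Preliminary PD date of 11.416.
2. Read PET and pMRI at every acquired follow-up visit up to and including the visit at which progression is confirmed.
3. For each progressor and each modality, classify the result as earlier than MRI, same visit, or later or not positive by the confirming visit. Report all three percentages, with the number of progressors as denominator.
4. Replace the paired t-test against conventional MRI with an exact two-sided sign test of earlier versus later. It uses direction only, so the end of reading at the confirming visit does not shrink the later cases relative to the earlier ones.
5. Keep the PET-versus-pMRI comparison. If Kaplan-Meier curves against MRI are kept, compute them on the full reading window and censor at the confirming visit any modality not positive by then.

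The cost is a change of wording and a little more reading of scans the trial already acquires. No new patients or scans are needed. The lead-time figure for PET and pMRI will be less favourable, but it can be interpreted.
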